2.1.6 Pharmacokinetic variables

The blood samples for the determination of functional sarilumab concentrations in serum will be collected before injection during the same visit according to the Study Flow Chart (refer to Section 1.2 in the study protocol) and at or near the onset and completion of the occurrence of a SAE. In addition, post-dose sample will be taken 4-7 days after the Week 24 (Visit 9).

2.1.7 Pharmacodynamic/genomics endpoints

Blood samples (DNA and genetic RNA) will be collected from each consenting patient to participate in the pharmacogenomics substudy. Details of any analysis will be described in a separate plan.

2.1.8 Other efficacy endpoints

Quality-of-life endpoints

Other efficacy endpoints in the clinical outcome assessments will be summarized. Patients are asked to complete the following patient-reported outcome (PRO) questionnaires described below at Visit 2 (baseline visit), Visit 6 (Week 12), Visit 9 (Week 24), and Visit 12 (Week 52).

Patient-Reported Outcomes

Short Form 36 Version 2 (SF-36 V2)

The SF-36 V2 is a multi-purpose, short-form health survey with 36 questions. It yields scores for eight domains (Physical Functioning, Role-Physical, Bodily pain, General health, Vitality, Social Functioning, Role-Emotional, and Mental Health, each scale is scored from 0 to 100 where higher scores indicate better health and well-being), as well as two summary measures of physical and mental health: the Physical Component Summary (PCS) and Mental Component Summary (MCS).

The scoring process is summarized below:

- Enter item response data.
- Recode item response values.
- Determine health domain scale raw scores.
- Transform health domain scale raw scores to 0 to 100 scores.
- Transform health domain scale 0 to 100 to normal-based scores.
- Score physical and mental component summary measures.

The following table shows the construction and summary measures of the SF-36 scales:

Table 4 – SF-36 V2 measurement model

Summary measures	Scales	Items
Physical Component Summary (PCS)*	Physical Functioning (PF)	3a, 3b, 3c, 3d, 3e, 3f, 3g, 3h, 3i, 3j
	Role-Physical (RP)	4a, 4b, 4c, 4d
	Bodily Pain (BP)	7, 8
	General Health (GH)	1, 11a, 11b, 11c, 11d
Mental Component Summary (MCS)*	Vitality (VT)	9a, 9e, 9g, 9i
	Social Functioning (SF)	6, 10
	Role-Emotional (RE)	5a, 5b, 5c
	Mental Health (MH)	9b, 9c, 9d, 9f, 9h

*MCS and PCS derived from the eight scales

The score of each of the 36 items is collected in CRF. [Appendix H](#) provides the SAS code to calculate the eight scales, the two summary measure scores and the standardized summary scores.

The PCS and MCS summary measure scores will be computed if at least 50% of the component scales are available. The scale scores will be computed if at least 50% of items are available within the corresponding scale. The missing items will be imputed by the mean of available items.

Change from baseline in SF-36 scores (physical component summary score and mental component summary score as well as the eight domains) at each visit will be analyzed.

Functional Assessment of Chronic Illness Therapy Fatigue (FACIT-Fatigue)

The FACIT-Fatigue will be used to assess fatigue. The FACIT-Fatigue is a 13-item questionnaire rated 0 to 4 originally developed to measure fatigue in patients with cancer and is widely used in rheumatoid arthritis patients to demonstrate good consistency and sensitivity to change. The patient will be asked to answer 13 questions rated 0 to 4 (0 = not at all, 1 = a little bit, 2 = somewhat, 3 = quite a bit, 4 = very much). The fatigue scale has 13 items, with 52 as the highest possible score. A higher score in the fatigue scale corresponds to a lower level of fatigue and indicates better Quality of Life.

To calculate the FACIT-fatigue score, the response scores on negatively phrased questions are reversed and then the 13 item responses are added. Eleven items with responses have their scores reversed (item score = 4 – response, if the response is not missing), and two items (items 7 and 8) have their responses unchanged ([Appendix F](#)). All items are added so that higher scores correspond to less fatigue. In cases where individual questions are skipped, scores are prorated using the average of other answers in the scale.

FACIT-Fatigue = 13 * [sum (reversed items) + sum (items 7 and 8)] / number of answered items

EuroQol 5 Dimension 3 Level (EQ-5D-3L)

The EQ-5D-3L is a standardized, generic measure of health outcome (3). EQ-5D is designed for self-completion by patients. Instructions to respondents are included in the questionnaire. The EQ5D is specifically included to address concerns regarding the health economic impact of RA, which have been considered in cost effectiveness arguments. The EQ-5D-3L comprises five questions on mobility, self-care, pain, usual activities, and psychological status with three possible answers for each item (1 = no problem, 2 = moderate problems, 3 = severe problems) and a vertical visual analog scale that allows the patients to indicate their health state today that can range from 0 (worst imaginable) to 100 (best imaginable).

The 5 dimensional 3-level systems are converted into a single index utility score. Values for the 243 theoretically possible health states defined by the EuroQol classification are calculated using a regression model and weighted according to the social preferences of the GB population. The minimum value for the single index utility score is -0.594, which corresponds to a level 3 (severe problems) for mobility, self-care, usual activities, pain/discomfort and anxiety/depression. The maximum value for this index is 1.0, which corresponds to a full health (level 1 [no problem] for mobility, self-care, usual activities, pain/discomfort and anxiety/depression).

The VAS records the respondent's self-rated health on a vertical visual analogue scale. The VAS "thermometer" has endpoints of 100 (Best imaginable health state) at the top and 0 (Worst imaginable health state) at the bottom. This information can be used as a quantitative measure of health outcomes as judged by the individual respondents. EQ 5D self-reported VAS data generates information on the self-perceived overall health-related quality of life.

[Appendix G](#) provides the SAS code to derive the index utility score using GB based population.

Health Assessment Questionnaire Disease Index (HAQ-DI)

- ***Patient's Assessment of Physical function***

The HAQ-DI is a standardized questionnaire developed to assess physical functional status in adults with arthritis but is now commonly used among many rheumatologic conditions. The HAQ-DI, with the past week as the time frame, focuses on whether the respondent "is able to..." do the activity and covers eight categories in 20 items: dressing and grooming, arising, eating, walking, hygiene, reach, grip and activities, for which there are at least two questions by category. The four responses for the HAQ-DI questions are graded as follows: without any difficulty=0;

with some difficulty=1; with much difficulty=2; and unable to do=3. To calculate the Standard HAQ-DI Score (With Aids/Devices), there are 3 steps:

1. Sum the eight category scores by using the highest sub-category score from each category.
 - For example, in the category EATING there are three sub-category items. A patient responds with a 1, 2, and 0, respectively; the category score is 2.
2. Adjust for use of aids/devices and/or help from another person when indicated.
 - When there are NO aids or devices or help indicated for a category, the category's score is not modified.
 - When aids or devices or help ARE indicated by the patient:
 - Adjust the score for a category by increasing a 0 or a 1 to a 2.
 - If a patient's highest score for that sub-category is a 2 it remains a 2, and if a 3, it remains a 3.
 - The data entered at field "Other specify" will not be used for score adjustment.
3. Divide the summed category scores by the number of categories answered (must be a minimum of 6) to obtain a HAQ-DI score of 0 to 3 (3=worst functioning).

A HAQ-DI score cannot be calculated validly when there are scores for less than six of the eight categories. If there are less than 6 categories completed, a HAQ-DI cannot be computed, whether the missing categories are due to missing values or they do not apply to the respondent. HAQ-DI disability index scoring ranges between 0 and 3 with higher score indicating greater disability. A high HAQ-DI score has been found to be a strong predictor of morbidity and mortality in RA. A 0.22 unit difference is considered clinically meaningful.

In addition to the above, the HAQ-DI has two additional questions to measure pain and global assessment described below.

- **Patient's Assessment of Pain**

Patients will be requested to indicate their pain intensity due to PMR using a 100 mm horizontal VAS to the question "*How much pain have you had IN THE PAST WEEK?*", where 0 is considered "No pain" and 100 "the worst pain you can imagine".

To obtain the patient score, using a metric ruler, measure the distance in centimeters from the left anchor (at base zero) to their mark and multiply by 0.2. This converts the number of centimeters into the appropriate score and yields a score from 0 to 3. For example, the mark is at 8 centimeters – $8 \times 0.2 =$ a pain score of 1.6.

In case a 0-100 mm scale is used, pain severity coding translations follow below:

PAIN SEVERITY CODING TRANSLATIONS

Measurement (m) = Score	Measurement (m) = Score [continue]
0 = 0	7.8 – 8.2 = 1.6
0.1 – 0.7 = 0.1	8.3 – 8.7 = 1.7
0.8 – 1.2 = 0.2	8.8 – 9.2 = 1.8
1.3 – 1.7 = 0.3	9.3 – 9.7 = 1.9
1.8 – 2.2 = 0.4	9.8 – 10.2 = 2.0
2.3 – 2.7 = 0.5	10.3 – 10.7 = 2.1
2.8 – 3.2 = 0.6	10.8 – 11.2 = 2.2
3.3 – 3.7 = 0.7	11.3 – 11.7 = 2.3
3.8 – 4.2 = 0.8	11.8 – 12.2 = 2.4
4.3 – 4.7 = 0.9	12.3 – 12.7 = 2.5
4.8 – 5.2 = 1.0	12.8 – 13.2 = 2.6
5.3 – 5.7 = 1.1	13.3 – 13.7 = 2.7
5.8 – 6.2 = 1.2	13.8 – 14.2 = 2.8
6.3 – 6.7 = 1.3	14.3 – 14.7 = 2.9
6.8 – 7.2 = 1.4	14.8 – 15.0 = 3.0

- **Patient’s Global Assessments of Disease Activity**

Patient’s global assessments of their current disease activity will be rated on an anchored 100 mm horizontal VAS, with the given instruction to “*Please rate how well you are doing on a scale of 0 to 100 (0 represents “very well” and 100 represents “very poor” health)*”.

It is scored similarly to the VAS Pain Scale.

Clinician-Reported Outcomes

Physician’s Global Assessments of Disease Activity – Visual Analog Scale [MD-VAS]

Physician’s global assessments of the patient’s current disease activity will be assessed on an anchored 100 mm horizontal VAS where 0 is considered the best disease activity (no disease activity) and 100 the worst (most disease activity).

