##### 9.3.1.1.4 *HAQ-DI*

The HAQ-DI was developed to assess physical functional status in adults with arthritis but is now commonly used among many rheumatologic conditions. It contains 25 items: 20 4-point Likert-scale questions assessing 8 physical dimensions of activities of daily living (dressing and

grooming, arising, eating, walking, hygiene, reaching, gripping, and errands and chores), 13 additional questions assessing use of assistive devices, and 8 additional questions assessing help received from another. The recall period is the last week. To calculate the HAQ-DI Score, there are 3 steps:

1. Sum the 8 category scores by using the highest sub-category score from each category.
2. Adjust for use of aids/devices and/or help from another person when indicated.
3. Divide the summed category scores by the number of categories answered (must be a minimum of 6) to obtain a HAQ-DI score of 0-3 (3=worst functioning).

In addition to the above, the HAQ-DI has two additional questions, measured on 0-100 scales:

- How much pain have you had IN THE PAST WEEK?
- Please rate how well you are doing on a scale of 0 to 100 (0 represents “very well” and 100 represents “very poor” health).

These questions, measuring pain and global assessment respectively, are independently scored. Refer to [Appendix K](#).

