2.1.3.3 Exploratory endpoint(s)

Following recommendation from the meeting with Japan Health Authority (PMDA) in April 2019, exploratory analysis will be performed for disease activity in PMR, quantified by the PMR activity score (PMR-AS).

PMR-AS is calculated as: CRP (mg/dl) + VAS p (0-10) + VAS ph (0-10) + (MST (min) x 0.1) + EUL (3-0).

Visual analogue scale for pain (VAS p) is the patient’s assessment of pain from HAQ-DI assessment, and the visual analogue scale for physician’s assessment (VAS ph) is the physician’s global assessment of disease activity, MD-VAS. The exact duration of morning stiffness (MST) and the ability to elevate the upper limbs (EUL: 3 = none, 2 = below shoulder girdle, 1 = up to shoulder girdle, 0 = above shoulder girdle) are captured in the “PMR assessment” eCRF. CRP value is from laboratory measurements.

PMR-AS will be assessed at baseline, Week 12, Week 24, and Week 52.

Note that only binary MST duration was collected (≤ 45 mins OR > 45 mins) prior to the collection of exact MST duration implemented in June 2019. Missing exact MST duration will be imputed using the median of MST duration at visit for each MST category (≤ 45 mins and > 45 mins).

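### SAP 2.1.8 scores HAQ-DI pain and patient global inconsistently: centimetres × 0.2 on the stated 100 mm line gives at most 2.0, not the stated 3

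*SAP*

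**What the plan says.** For pain, SAP 2.1.8 fixes the instrument: "Patients will be requested to indicate their pain intensity due to PMR using a 100 mm horizontal VAS". To score it, the analyst is to take the distance of the mark from the left end in centimetres and "multiply by 0.2. This converts the number of centimeters into the appropriate score and yields a score from 0 to 3". Its worked example turns a mark at 8 cm into 1.6. A translation table follows, introduced as the one for a 0-100 mm scale. It gives 2.0 for readings of 9.8 to 10.2 and ends at 3.0 for readings of 14.8 to 15.0.

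Patient global is also on a 100 mm line, with a 0 to 100 rating instruction, and the SAP adds: "It is scored similarly to the VAS Pain Scale".

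Protocol 9.3.1.1.4 says that "the HAQ-DI has two additional questions, measured on 0-100 scales" and that each is scored on its own. It gives no conversion to 0-3.

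Both items are among the other efficacy endpoints. SAP 2.4.7 analyses change from baseline at Week 52 by MMRM and reports LS means, the difference between groups, its 95% confidence interval and a p-value.

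**The concern.** The line length, the multiplier and the resulting range cannot all be right. A patient who marks the extreme right of a 10 cm line scores 2.0, and nobody can score higher. The factor 0.2 and the end point of the table both fit a 15 cm line.

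What is at stake is the unit in which two analysed endpoints are reported. A reader told that pain runs from 0 to 3 would judge the LS means, the treatment difference and its interval against that range, when the scores in fact run from 0 to 2. Comparison with HAQ pain scores that do run from 0 to 3 would be off by the same ratio.

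**Working it through.** **Inputs, all from SAP 2.1.8.** Line length 100 mm = 10 cm; factor 0.2 per cm; stated range 0 to 3; table rows 9.8-10.2 → 2.0 and 14.8-15.0 → 3.0.

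**1. Reproduce the SAP's figures.** Score = centimetres × 0.2.
- Worked example: 8 × 0.2 = 1.6. This reproduces.
- Stated maximum of 3 on a 10 cm line: 10 × 0.2 = 2.0. This does not reproduce.
- The same rule on a 15 cm line: 15 × 0.2 = 3.0. This does.

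**2. Check the table.** It follows the same rule, rounded to 0.1: the row centred on 8.0 gives 8.0 × 0.2 = 1.6, the row centred on 10.0 gives 10.0 × 0.2 = 2.0, and the last row gives 15.0 × 0.2 = 3.0. A 10 cm line therefore stops at 2.0, and the ten rows from 2.1 to 3.0 can never be used.

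**3. Factor needed for 0-3.** Factor = 3 / line length. For 10 cm this is 3/10 = 0.3; for 15 cm it is 3/15 = 0.2.

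**4. Size of the shortfall on a 10 cm line.** 0.2/0.3 = 0.667, so results are one third smaller than on a true 0-3 scale.

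| Mark or difference | As written (× 0.2) | True 0-3 (× 0.3) |
|---|---|---|
| 2 cm | 0.40 | 0.60 |
| 8 cm | 1.60 | 2.40 |
| 10 cm | 2.00 | 3.00 |

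**5. Effect on inference.** Multiplying the outcome and its baseline covariate by one constant multiplies the estimate, its standard error and the confidence limits by that constant. The test statistic, p-value and standardised effect stay the same. As an illustration, two groups of 59 were simulated on a 10 cm line (assumed means 4 and 5.2 cm, SD 2.5 cm, truncated to 0-10) and compared by t test. The difference was -0.224 with factor 0.2 and -0.336 with factor 0.3, with p = 0.0035 both times. Using the table instead gave -0.227, or 0.676 of the 0.3 value, so its rounding changes little.

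**The case against.** The strongest reply is that nothing is biased. A constant factor rescales baseline, means, differences and limits together, and the tests do not notice. Only two endpoints are involved, and neither is in the testing sequence of SAP 2.4.4.4, which runs from the primary endpoint to cumulative corticosteroid dose. This stands, and it limits the point to reporting units.

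It can also be said that the direction of the error is not settled. If the line used was 15 cm, then 100 mm is the slip and nothing shrinks. In addition, the protocol appendices say that the paper questionnaires will be adapted for electronic use, so a rule based on a metric ruler may be leftover text that is never applied. Both are possible, although the protocol's 0-100 scales and the SAP's own 100 mm descriptions point to a 100-unit line. In each case the SAP text still needs correcting, because its three statements conflict.

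Three stronger readings are tempting but not supported:
- A reader might infer that every patient-reported effect is too small. The HAQ-DI disability index, SF-36, EQ-5D-3L, FACIT-Fatigue and MD-VAS have their own scoring and are not touched.
- A reader might infer that the 0.22 clinically meaningful difference in SAP 2.1.8 would be misapplied. That figure is stated for the disability index, not for these two items.
- A reader might infer that the PMR activity score is wrong because it uses the same pain item. SAP 2.1.3.3 begins its formula "PMR-AS is calculated as: CRP (mg/dl) + VAS p (0-10) + VAS ph (0-10" and so already requires pain on 0-10. MD-VAS, also collected on 100 mm, enters on 0-10 too, which implies division by 10 for both. A pain input running only to 2 would contradict that text.

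**Conclusion.** The scoring rule for HAQ-DI pain and patient global is wrong as written. On the stated 10 cm line its ceiling is 2.0 against a stated 3, and the accompanying table fits a 15 cm line.

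If the rule or the table is applied to a 10 cm line, LS means, treatment differences and confidence limits for these two endpoints are two thirds of their size on the stated 0-3 scale, apart from small rounding from the table. That figure rests on literal use of the 0.2 factor and on the line really being 100 mm; with a 15 cm line there is no shortfall. P-values, standardised effects, the disability index and the primary endpoint are unaffected, and no error in the PMR activity score is shown. The correction is still worth making: the defect is certain on the SAP's own text, it changes reported numbers, and it is almost free to repair.

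**What to change.** - Preferred: analyse and report both items on the 0-100 scale in Protocol 9.3.1.1.4, and remove the conversion from SAP 2.1.8.
- If a 0-3 score is wanted: use 0.3 per cm (0.03 per mm) for the 100 mm line, and change the worked example to 8 × 0.3 = 2.4.
- In either case, delete the table that runs to 15.0, or replace it with one that matches the chosen rule. Confirm the line or response range actually used against the HAQ-DI form as administered.
- Label the scale range in the output tables for both items.
- Optional: add to SAP 2.1.3.3 that the PMR activity score takes the 0-100 VAS divided by 10.

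The cost is SAP wording and one line of programming. No new data are needed.

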2.2 DISPOSITION OF PATIENTS

This section describes patient disposition for both patient status and the patient populations.

Screened patients are defined as all patients who signed the informed consent.

Randomized patients consist of all patients who signed informed consent with a treatment kit number allocated and recorded in the Interactive Voice Response System/Interactive Web Response System database, regardless of whether the treatment kit was used or not.

For patient status in the DB treatment period, the total number of patients for each one of the following categories will be presented in the clinical study report (CSR) using a summary table:

- Screened patients
- Screen failure patients and reasons for screen failure
- Non-randomized but treated patients
- Randomized patients
- Randomized but not treated patients
- Randomized and treated patients
- Patients who completed 52-week SC IMP study treatment period
- Patients who discontinued from 52-week study treatment period and the reasons for permanent SC IMP treatment discontinuation
- Patients who completed the study
- Patients who discontinued the study and the reasons for study discontinuation
- Patients who took CS rescue therapy
- Patients who took add-on prednisone
- Subject status at end of study visit

For all categories of patients (except for the screened and non-randomized categories) percentages will be calculated using the number of randomized patients as the denominator. Reasons for SC IMP treatment or study discontinuation, such as if it is related to COVID-19 will be presented in tables giving numbers and percentages by treatment group. Patient disposition by visit according to trial impact due to COVID-19 (visits that were delayed, not done, partially done on site, or partially done by phone, or not impacted) will also be provided.

A patient is considered as lost to follow-up at the end of the study if he/she is not assessed at the end of study visit.

All critical or major deviations potentially impacting efficacy analyses, randomization and drug dispensing irregularities and other major/critical deviations will be summarized in tables giving numbers and percentages of deviations by treatment groups. Critical or major deviations according to COVID19 impact will also be summarized.

Additionally, the analysis populations for safety, efficacy, PK and immunogenicity will be summarized in a table by patient counts based on the randomized populations (See definitions in [Section 2.3](#)).

- Efficacy population
- Safety population
- PK population

- ADA population

2.2.1 Randomization and drug dispensing irregularities

Randomization and drug-dispensing irregularities occur whenever:

1. A randomization is not in accordance with the protocol-defined randomization method, such as a) an ineligible patient is randomized, b) a patient is randomized based on an incorrect stratum, c) a patient is randomized twice, or d) in a dynamic randomization scheme the treatment assignment is, in fact, not random, due to a computer program error.

OR

2. A patient is dispensed an IMP kit not allocated by the protocol-defined randomization, such as a) a patient at any time in the study is dispensed a different treatment kit than as randomized (which may or may not contain the correct-as-randomized IMP), or b) a nonrandomized patient is treated with IMP reserved for randomized patients.

Randomization and drug-dispensing irregularities will be monitored throughout the study and reviewed on an ongoing basis.

All randomization and drug-dispensing irregularities will be considered as protocol deviations and documented in the CSR. If the number of irregularities is large enough to make a tabular summary useful, the irregularities will be categorized and summarized among randomized patients (number and percentages). Nonrandomized, treated patients will be described separately.

Randomization and drug-dispensing irregularities to be prospectively identified include but are not limited to:

Table 5 – Randomization and Drug Allocation Irregularities

Randomization and Drug Allocation Irregularities
Kit dispensation without IVRS transaction
Erroneous kit dispensation
Kit not available
Randomization by error
Subject randomized twice
Forced randomization
Subject switched to another site

IVRS=Interactive Voice Response System

